[figure not shown]
- 1] Adverse Events (AEs) – within 4 weeks of treatment as judged by **blinded** physician reviewers to be possibly related to the study drug(s).
- 2] Parasite clearance time – time from the initiation of treatment to the first of 2 successive negative thick smears.
- 3] Time to recrudescence or reinfection – time from the initiation of treatment to the reappearance of asexual *P. falciparum* parasites on the thick smear.
- 4] Effects on the QT (QTc) interval – mean changes from the baseline (pre-treatment) QTc interval to the post-treatment QTc interval after treatment with AQ-13 or Coartem.
- 5] Pharmacokinetic parameters for AQ-13 – will include measurements of AQ-13 blood levels over time (peak levels, AUC, MRT), drug distribution (Vd/F) and drug elimination (t $\frac{1}{2}$, Cl/F).
- 6] Fever clearance time: time in hours from the initiation of therapy until the disappearance of fever for at least 24 hours.

Tertiary Objectives and associated Endpoints for comparisons of AQ-13 with Coartem:

- 1] Pharmacokinetics of AQ-13 metabolites – estimates of pharmacokinetic parameters for the mono- and di-*N*-dealkylated metabolites of AQ-13 (AQ-72, AQ-73).
- 2] Aminoquinoline (CQ) pruritus – pruritus in persons receiving AQ-13 or Coartem, especially in persons with a history of pruritus after treatment with CQ.

Schematic of Study Design (Flow Chart 1, below):

This is a **randomized study in which subjects** who have provided their informed consent to participate **will be randomized to one of two study arms**: 1] oral administration of AQ-13 (1596 mg AQ-13 base over 3 days) or 2] the control arm, in which subjects will receive the standard treatment dose of Coartem (artemether + lumefantrine; 4 tablets twice daily x 3 days) which is currently recommended as the first-line treatment for uncomplicated *P. falciparum* malaria in Mali, including infections likely to be resistant to chloroquine (CQ) or pyrimethamine + sulfadoxine (Fansidar[®]). This is a single-blind study because the subjects (**but not the investigators**) will know which subjects are receiving AQ-13 vs. Coartem (by the number and types of capsules [AQ-13] or tablets [Coartem]).

Flow Chart 1**PROOF OF CONCEPT EFFICACY STUDY FOR AQ-13**

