In addition, recent Phase 1 (safety and pharmacokinetic) studies have shown that the side effects (adverse events [AEs] associated with) of the lead compound AQ-13 (which has a linear *n*-propyl side chain) in human subjects are similar to those of CQ and that the pharmacokinetics of AQ-13 and CQ are similar [11]. In terms of potential cost, the current estimate of the cost of goods for AQ-13 is \$0.03 per dose (for an AQ-13 oral dose equivalent to 700 mg CQ base in terms of bioavailability), which is approximately \$0.08 per treatment course if the treatment dose chosen is 1596 mg over 3 days. In addition, the close structural similarity between AQ-13 and CQ and the similar Adverse Events (AEs) observed with AQ-13 and CQ in the Phase 1 studies [11] suggest that AQ-13 may be as safe as CQ for the treatment of human subjects with malaria, and raise the possibility that AQ-13 may share the safety of CQ during pregnancy. Although these arguments are part of the rationale for studying AQ-13, please note that **adult women (including women who are pregnant or breast-feeding) are excluded from participation in these studies**. Finally, please note that AQ-13 is only one of 66 AQs which we have synthesized and shown to be active against CQ- and multi-resistant *P. falciparum* [9-10]. Therefore, if these studies are successful, they have the potential to create a new class of AQ antimalarials effective against otherwise drug-resistant *P. falciparum* malaria parasites.

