Safety Oversight will be assisted by a Data Safety and Monitoring Board (see section 8.7 on page 33, below).

Flow Chart 2

PROOF OF CONCEPT STUDY FOR AQ-13 ADULT MALES WITH UNCOMPLICATED *P. falciparum* MALARIA

Recruitment in the Villages of Missira and Sirakoroba in Northwestern Mali
and from Outpatient Referral Clinics in the city of Bamako;

In-Patient Studies at the Clinical Research Center, Hôpital Point G in Bamako

Flow Chart 3**PROOF OF CONCEPT STUDY FOR AQ-13
RANDOMIZATION, DRUG ADMINISTRATION AND FOLLOW-UP**

Recruitment in the Villages of Missira and Sirakoroba in Northwestern Mali

and from Outpatient Referral Clinics in the city of Bamako;

In-Patient Studies at the Clinical Research Center, Hôpital Point G in Bamako

EYE EXAMS, HOLTER RECORDINGS, CHEMISTRY PANEL, HEMATOLOGY (CBC)
(n=70; 35 each for the AQ-13 and Coartem groups, expected 5% ineligible).

•INCLUSION CRITERIA:

≥ 2,000 asexual *P. falciparum* parasites per μ l,
Uncomplicated *P. falciparum* malaria,

•Baseline Screening Holter Recording x 1 hour,**•Visual Screening** baseline acuity, visual fields,**•EXCLUSIONS:** Hb ≤ 7 gms/dL, K+ ≤ 3.5 mEq/L, arrhythmias, heart block, BP ≥ 140/90 or severe or complicated malaria.

RANDOMIZE ELIGIBLE ADULT VOLUNTEERS WITH UNCOMPLICATED *P. falciparum* MALARIA
(n=66; 33 each for the AQ-13 and Coartem groups, expected 20% loss to follow-up).

•Filter Paper Blots for molecular studies,**•Freeze Initial Parasites** at -70° C,**•pfcr PCR and other Tests** for CQ Resistance,**•Oral Administration of 700 mg AQ-13 on days 1-2,** followed by 350 mg on day 3, OR

Oral Administration of Coartem, 80 mg artemether

+ 480 mg lumefantrine twice daily x 3 days,

•Repeat Daily Blood Smears (days 1 through 7), repeat Hematology, Chemistry panels on day 4,**•AQ Drug and Metabolite Levels** at 0, 0.5, 1, 2, 4, 6, 12, 18, 24, 24.5, 25, 26, 28, 30, 36, 48, 48.5, 49, 50, 52, 54, 60, 72, 96 and 120 hours x 5 ml,**•Holter Monitoring** 24 hours/day x 4 inpatient days,**•One Week** eye exam, 1 hour Holter recording,**•WITHDRAWAL:** severe or complicated malaria.

FOLLOW-UP
for a total of 6 weeks,
PRIMARY ENDPOINT is
a lack of recrudescence
with the same genotype(s)
(n=28 evaluable subjects/group)

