6 STUDY PROCEDURES/EVALUATIONS

Table 1.

Study Schedule: PROOF OF CONCEPT EFFICACY STUDY OF AQ-13

Activity, Day(s) Tests Performed and Potential Findings

DIAGNOSIS, Day 1: Malian males ≥ 18 years with Fever and Chills	Blood smear to diagnose malaria in an adult Malian male is positive (and the subject fulfills none of the exclusion criteria)
INVITATION, Day 1: Invite to Participate in Study of AQ-13	Decide whether to participate in the Phase 2 Proof of Concept Study of AQ-13 by providing informed consent
SCREENING, Day 1: Subjects with malaria who provide consent	Screening 1 hour Holter recording, 2 tubes of blood for chemistry and hematology testing, eye examination
ENROLLMENT, Day 1: Randomize eligible, consented subjects	Randomization of subjects to AQ-13 (1596 mg orally over 3 days) or to the control arm, Coartem (4 tabs x 2/day x 3 days)
INPATIENT STUDIES: Days 1-7	Blood samples for drug and metabolite levels on days 1-5; Two tubes of blood for hematology and chemistry panels on day 4; 24 Holter recordings on dosing days 1-4; Urine collections on days 1-4; Eye exam plus an additional Holter recording at the end of week 1.
OUTPATIENT FOLLOW-UP, Days 8-42: (Weeks 2-6)	Five weeks of outpatient follow-up with 2 visits each week, to obtain 1 tube of blood for drug and metabolite levels on both visits in week 2, and 1 tube per week (at 1 of the 2 outpatient visits) in weeks 3 to 6; During week 2, there is a repeat 1 hour Holter recording and a review (discussion) of potential side effects (AEs).

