6.8 Discontinuation or Withdrawal of a Subject

Treatment with AQ-13 or Coartem in this study may be discontinued for any of the reasons below. However, whenever possible (i.e., except when informed consent to participate has been withdrawn) subjects will be followed through to the conclusion of the treatment of their illness and outcomes will be examined using both *intent to treat* and *per protocol* analyses.

- 1] Recurrence of uncomplicated malaria,
- 2] Progression to severe or complicated malaria,
- 3] Development of ventricular tachyarrhythmias or conduction defects (new 2nd or 3rd degree heart block),
- 4] Other Serious Adverse Events (SAEs) possibly related to AQ-13, or
- 5] The subject's decision to withdraw his/her informed consent to participate.

If lack of cure (recurrence of uncomplicated malaria) occurs with either AQ-13 or Coartem, the subject will be treated with Quinine. Likewise, if a subject develops severe or complicated malaria, he will be treated with Quinine as recommended by the Mali Ministry of Health and the National Malaria Control Programme. Treatment with either AQ-13 or Coartem will be stopped in subjects who develop ventricular tachyarrhythmias, conduction defects or other serious adverse events (SAEs) possibly related to AQ-13 or Coartem. In those instances, further antimalarial treatment (if necessary) will be provided using Quinine based on the recommendations of the Mali Ministry of Health and the Mali National Malaria Control Programme.

Flow Chart 4.Work Sheet (schedule of procedures) for Phase 2 efficacy studies of AQ-13 in semi-immune Malian adult Males ≥ 18 years of age

Clinical	Scr	Pre-dose	0	30 m	1 hr	2	4	6	12	18	24	24:30	25	26	28	30	36	48	48:30	49	50	52	54	60	72	96	1/2 wks	
History/PE	X																										X	
Medication History	X																										X	
Assess for AEs		X							X										X						X		X ₁	
Laboratory																												
CBC,WBC, diff, plt	X																										X	
Chem 7	X																										X	
Liver profile	X																										X	
G6PD	X																											
AQ & Metabolites			X	X	X	X	X	X	X	X	X	X	X	X	X	X	X	X	X	X	X	X	X	X	X	X		
Freeze parasites			X																									
24 hr urine		X									X									X						X		
Diagnostics																												
Holter Recording	X		X ₂								X ₂								X ₂						X ₂		X ^{**}	
Eye exam	X																											X
Study Drug AQ-13 $\Sigma=1750$ mg			X ₃								X ₃								X ₃									

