Coartem X ₄ =4 tabs			X ₄						X ₄		X ₄							X ₄	X ₄						X ₄			

X1 – To be performed by study Co-Investigator while inpatient and at follow-up

X2 – To be done over 96 hours (4 days), beginning at zero time on day 1

X3 – AQ-13 dose; to be given in the morning x 3 days.

X4 – Coartem dose (4 tablets in morning and afternoon x 3 days).

½ wks – at the end of week 1 and the end of week 2

* - blood draws at 96 and 120 hours after this, then twice a week for 6 weeks.

** - Holter recording for 1 hour at 1 and 2 week follow up visits.

Table 3.

WEEK ONE BLOOD SAMPLING SCHEDULE FOR AQ-13 DRUG AND METABOLITE LEVELS

Days	Day 1								Day 2								Day 3								4	5	6	
Hours	0	0.5	1	2	4	6	12	18	24	24.5	25	26	28	30	36	48	48.5	49	50	52	54	60	72	96	120			

Gantt Chart**ORGANIZATION OF THE PHASE 2 PROOF OF CONCEPT STUDY OF AQ-13**

	OUTPT	INPT	INPATIENT WEEK 1							OUTPATIENT FOLLOW-UP (WEEKS 2 TO 6)					
Recruitment	X	TESTS													
Informed Consent	X														
Thick Smear	X		X	X	X	X	X	X	X	2 per Week	2 per Week	2 per Week	2 per Week	2 per Week	2 per Week
Thin Smear	X														
Filter Paper Blot	X		X	X	X	X	X	X	X	2 per Week	2 per Week	2 per Week	2 per Week	2 per Week	2 per Week
Physical Exam	X		X	X	X	X	X	X	X	2 per Week	2 per Week	2 per Week	2 per Week	2 per Week	2 per Week
Hb	X						X								
Transport Decision	X														
Hematology Panel			X				X								
Chemistry Panel	X						X								
Eye Examination	X								X						
Holter (1 hour)	X								X	Day 14					
Holter (24 hours)			X	X	X	X									
Randomisation	X														
Drug Treatment			X	X	X										
Pharmacokinetics			8	6	7	1	1	1		2 per Week	1 per Week	1 per Week	1 per Week	1 per Week	
Parasite Clearance									X						
End of Inpatient Stay									X						
Completion of Study															Day 42
	OUTPT	INPT	INPATIENT WEEK ONE							OUTPATIENT FOLLOW-UP (WEEKS 2 TO 6)					
	TESTS	TESTS	1	2	3	4	5	6	7	8 to 14	15 to 21	22 to 28	29 to 35	36 to 42	
	DAYS									2	3	4	5	6	
	WEEK														

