10.3 Analysis Plan

This is a Proof of Concept Efficacy Study of AQ-13 in comparison to the gold standard (Coartem). Thus, this study in adult Malian males can be viewed as a non-inferiority study, comparing one dose of AQ-13 (1596 mg orally over 3 days) to Coartem [39].

The null and alternative hypotheses to be tested are:

$$H_0 = (C - E) \geq M \quad (\text{control is superior to experimental})$$

$$H_1 = (C - E) < M \quad (\text{experimental is not inferior to control})$$

C is the efficacy of the comparator (Coartem), E the efficacy of the investigational drug (AQ-13) and M the non-inferiority margin. $M = 15\%$ will be used (see above). AQ-13 will be considered equivalent to (not inferior to) the comparator (Coartem) if the null hypothesis is rejected with a one-sided alpha of 0.025 [29, 40]. Cure rates, adjusted for reinfection, will be calculated for AQ-13 and Coartem and differences between cure rates with AQ-13 and Coartem will be calculated with 95% confidence intervals. Non-inferiority of AQ-13 will be established if the upper limit of the 95% CI for the difference between AQ-13 and Coartem is less than the non-inferiority margin of 15% [28-29].

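### The AQ-13 course is stated as 1596 mg in the text and analysis plan but as 1750 mg in Flow Charts 3 and 4, with no conversion given

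*Combined protocol and SAP*

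**What the plan says.** **1596 mg.** This total appears in ten places: the synopsis, the Schematic of Study Design, 2.1 Background, 2.2 Rationale, the Statement of Purpose in section 3, section 4, the enrolment paragraph of section 5.1, Table 1, and sections 10.2 and 10.3. Table 1 reads "Randomization of subjects to AQ-13 (1596 mg orally over 3 days", and section 10.3 describes the trial as "comparing one dose of AQ-13 (1596 mg orally over 3 days) to Coartem". Only the Schematic names a unit basis: "oral administration of AQ-13 (1596 mg AQ-13 base over 3 days".

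**1750 mg.** Flow Chart 3 gives "Oral Administration of 700 mg AQ-13 on days 1-2", "followed by 350 mg on day 3, OR" the Coartem regimen. The Flow Chart 4 work sheet carries the row label "Study Drug AQ-13 $\Sigma=1750$ mg". Its dosing footnote says "AQ-13 dose; to be given in the morning x 3 days" and gives no milligram amount.

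**The nearest thing to a link.** The cost sentence in section 2.1 prices a unit "for an AQ-13 oral dose equivalent to 700 mg CQ base in terms of bioavailability" and then the 1596 mg course. It does not say how many milligrams of AQ-13 that unit contains.

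**The concern.** The dose defines the intervention under test, and the current text gives two totals for it. The only day-by-day amounts are in Flow Chart 3, and they do not add up to the total in the hypotheses and analysis plan.

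Three uses of the dose are exposed:

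- **Supply and verification.** Section 9.1 has the monitor confirm that the product is supplied at the doses the protocol specifies. That needs one dose on one labelled basis.
- **Pharmacokinetics.** Cl/F and Vd/F are secondary endpoints and are proportional to the dose entered. The second hypothesis is that AQ-13 pharmacokinetics resemble Phase 1, and section 10.3 plans that comparison. A dose basis that differs between the two studies would bias it.
- **Later use.** Section 13.4 refers to children's doses scaled from adult doses in mg base per kg, yet only one statement of the adult amount is labelled as base. This lies outside the present trial and is a minor point.

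**Working it through.** **Inputs.** Flow Chart 3: 700 mg on each of days 1 and 2, 350 mg on day 3. Flow Chart 4: total 1750 mg. Text, Table 1 and analysis plan: 1596 mg. Section 2.1: $0.03 per unit and about $0.08 per course.

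**1. Reproduce the chart total.** 700 + 700 + 350 = 1750 mg. This matches Flow Chart 4 exactly and does not match 1596 mg.

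**2. Size of the gap on a common basis.**
- 1750 - 1596 = 154 mg
- 154 / 1596 = 9.6%
- 154 / 1750 = 8.8%
- 1596 / 1750 = 0.912

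**3. Is there a daily split for 1596 mg?** In Flow Chart 3's 2:2:1 proportions it would be 638.4 + 638.4 + 319.2 mg; in equal parts it would be 532 mg × 3. Neither set is printed anywhere. These figures are arithmetic only and are not proposed as doses.

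**4. Could the totals be one course in two units?** The linking factor would have to be 0.912. The text prints no such factor, and nothing labels 700, 350 or 1750 mg as salt or as a chloroquine equivalent. Flow Chart 3 simply calls its amount AQ-13.

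**5. Do the cost figures settle it?** Allowing for rounding, the number of units per course lies between 0.075 / 0.035 = 2.14 and 0.085 / 0.025 = 3.40.
- If the course is 1750 mg and the unit 700 mg on the same basis: 1750 / 700 = 2.50 units.
- If the course is 1596 mg and the unit is assumed to be 638.4 mg of AQ-13 (700 × 0.912): 1596 / 638.4 = 2.50 units.
- If the course is 1596 mg and the unit is assumed to be 700 mg of AQ-13: 1596 / 700 = 2.28 units. The text defines the 700 mg as chloroquine base, so this case needs an assumption the text does not make.

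All three lie inside the range, so the costs do not identify the unit basis.

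**6. Effect on the pharmacokinetic endpoints.** Cl/F = dose / AUC, and Vd/F = dose / (λ × AUC), where λ is the terminal rate constant. Both are proportional to the dose entered.
- 1750 entered when 1596 is true: 1750 / 1596 = 1.096, so both are 9.6% too high.
- 1596 entered when 1750 is true: 1596 / 1750 = 0.912, so both are 8.8% too low.

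Peak level, AUC, MRT and half-life come from the measured concentrations and do not change with the dose entered.

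**The case against.** The strongest reply is that this is one regimen in two units. The two charts agree with each other, and the ten text statements agree with each other. That pattern fits an unlabelled conversion at least as well as a dosing error. There is also only one daily schedule, so no two schedules compete at the bedside. Flow Chart 1 and some pages were not available for this review, and the Investigator's Brochure or Manual of Procedures may give a capsule strength or a salt/base note. Finally, a wrong dose basis in Cl/F and Vd/F can be corrected afterwards by a single factor, without new data.

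Much of this stands. The 9.6% is conditional on a common basis, a true difference of zero is possible, and nothing here shows that anyone was or would be given the wrong amount. The finding is limited to the text that could be read. But even if the two-unit reading is right, a reader cannot recover the conversion from that text, and the work-sheet total carries no unit basis. The pharmacokinetic error is correctable only once someone knows which basis was used, and no section names it.

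**Conclusion.** The concern holds: the dose is inconsistent as written and must be reconciled. Two totals, 1596 mg and 1750 mg, stand in current text with no stated relation. They differ by 154 mg (9.6% of 1596 mg) if they share a basis. If they do not, the difference may be zero, but a factor of 0.912 is then missing. The consequence is an unclear reference for supply and monitoring, and a possible systematic shift of +9.6% or -8.8% in Cl/F and Vd/F and in their comparison with Phase 1. More patients would not remove that shift. Sample size, non-inferiority margin, alpha and the comparison of cure rates by arm do not depend on the total.

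The conclusion rests on the text available. A conversion printed in Flow Chart 1 or a removed page would answer the missing-link point, though the two totals would still need labelling. No view is taken on which figure is correct.

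**What to change.** The sponsor should reconcile Flow Charts 3 and 4 with the ten statements of 1596 mg listed above. The result should be:

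1. One total course amount and one daily schedule that sums to it, identical in the text, Table 1, both flow charts and section 10.
2. A stated unit basis (base, salt or chloroquine equivalent) wherever an amount appears, or one definition that governs all of them, with any conversion factor printed.
3. One sentence in section 10.3 naming that basis as the dose input for Cl/F and Vd/F, and confirming that the Phase 1 values used for comparison are on the same basis.

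The cost is a correction to the text and work sheet plus one analysis sentence, with no added patients, visits or procedures. Section 13.2 requires ethics approval of any amendment before use. If reconciliation changes an amount actually given, rather than its label, the amendment is substantive and not clerical.

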5 STUDY POPULATION

5.1 Selection of the Study Population

The population to be studied is the subset of adult Malian males with uncomplicated *P. falciparum* malaria. There are two rationales for this choice. The first is that uncomplicated malaria with asexual parasite counts $\geq 2,000$ per μl is extremely common in Mali (affecting $\geq 40\text{-}90\%$ of the population in the transmission season). The second is that adults in Mali have acquired the semi-immune state and will therefore have an extremely low risk of severe or complicated malaria if AQ-13 is not effective for the treatment of uncomplicated malaria (which we do not expect to be the case).

Target Sample Size, including the actual numbers to be enrolled. The target sample size for the number of evaluable subjects is 28 evaluable subjects in each of 2 study arms for a total of 56 evaluable subjects. However, the numbers of potential subjects that will be recruited are greater than 28 per arm because of expected losses from: 1] persons who have a negative blood smear for malaria parasites, 2] the need to spend one week (5-7 days) at the Clinical Research Center during the inpatient phase of the study, 3] the subsequent 5 weeks of twice-weekly outpatient follow-up visits and 4] the multiple blood samples, monitoring and urine collections required for participation.

Numbers of subjects (adult males) that will be recruited. For the reasons outlined above and in Flow Charts 2-3 (pages 16-17), we expect to recruit 132 men (adult Malian males ≥ 18 years of age) thought to have uncomplicated malaria to identify 118 eligible men (who have positive smears with $\geq 2,000$ asexual parasites per μl and no other medical conditions that require diagnosis or treatment) in order to obtain 70 men willing to provide their informed consent to enroll and participate in the inpatient studies (33 per arm for the 2 study arms). Based on an additional 20% attrition during inpatient and outpatient follow-up, this should yield approximately 28 evaluable subjects per study arm (based on approximately 56 evaluable subjects from the initial 132 who were recruited and the 70 who provided their informed consent to participate in the study).

Indicate the source/site from which the study population will be drawn. The study population of Malian adult males with uncomplicated malaria will be drawn from several outpatient sites: 1] the Missira Community Health Center which serves the adjacent communities of Missira and Sirakoroba 160-170 km northwest of Bamako that have an estimated population of 6,000, and 2] referral clinics in urban and peri-urban Bamako, where >100 outpatients from the urban and peri-urban areas in and around Bamako seek treatment for uncomplicated malaria every day between August and November.

Identify strategies for subject recruitment and retention. Subjects will be recruited from persons who come to the Missira Community Health Center or to clinics that refer to the University of Bamako for the diagnosis and treatment of presumed uncomplicated *P. falciparum* malaria (fever, chills, headache, without signs or symptoms of severe or complicated malaria) [23]. We expect that close personal care and attention during the inpatient week of the study will minimize attrition during that time. To maximize cohort retention for the twice-weekly outpatient follow-up visits during the subsequent 5 weeks, we will provide financial compensation (CFA 5,000=\$10 US) for each outpatient visit and transportation home at the conclusion of each follow-up outpatient visit.

Ability to accomplish participant enrollment and Follow-Up

As noted above and in Flow Charts 2-3, this study is based on the analysis of approximately 28 evaluable subjects in each of the 2 study arms (28 x 2 = 56), and therefore on ≥ 56 evaluable subjects completing the study protocol. To achieve that goal, we expect to screen and enroll substantially greater numbers of subjects. Based on the number of subjects seeking diagnosis and treatment for uncomplicated malaria at the two recruitment sites (≥ 200 per month) and on the inpatient capacity of the Clinical Research Center at the Hôpital Point G (8-10 inpatients), it should be possible to accomplish this study and determine whether the 1596 mg dose of AQ-13 is as effective as Coartem for treatment of uncomplicated malaria.

As described above (on page 18) in the section on subject recruitment and retention), the majority of the subjects for this study will be recruited because they came to the Missira Community Health Center or a referral outpatient clinic in Bamako, requesting studies to diagnose and medicines to treat uncomplicated malaria. For those subjects, the initial screening malaria smear and rapid Hb determination are part of their routine clinical care. However, if it is necessary to recruit additional subjects from the community, a protocol amendment will be prepared in order to obtain a separate informed consent before performing a malaria smear, Hb determination or other studies potentially related to this Phase 2 Proof of Concept Efficacy Study of AQ-13. As noted below, and in the enclosed Gantt Chart (page 27), informed consent will be obtained before subjects are considered for the initial referral and transportation from Missira or other sites to the Clinical Research Center in Bamako.

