5%	235	261	294
7.5%	104	116	130
9%	73	81	91
10%	59	66	74
15%	26	29	33
20%	15	17	19

Although the sample size calculation was based on the primary endpoint of cure for all patients, based on studies we have performed in Mali previously, we expect that approximately 65% of the 26 evaluable subjects in each group will have CQ-resistant *P. falciparum* [35]. Therefore, subgroup analysis according to chloroquine susceptibility should make it possible to generate hypotheses about the efficacy of AQ-13, compared to Coartem, for subjects with either CQ-resistant or –susceptible parasites.

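### The stated 28 evaluable men per arm (56 in total) does not follow from the protocol's own funnel: 33 randomised per arm with 20% loss gives about 26

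*Combined protocol and SAP*

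**What the plan says.** Section 5.1 sets an evaluable target of 28 per arm, 56 in total, and describes how it will be reached. The sponsor writes "we expect to recruit 132 men" and, from that number, plans "to identify 118 eligible men". The consent stage is then described as "70 men willing to provide their informed consent to enroll and participate in the inpatient studies (33 per arm for the 2 study arms"). On what follows consent, the section states: "Based on an additional 20% attrition during inpatient and outpatient follow-up, this should yield approximately 28 evaluable subjects per study arm". The same sentence names the 132 recruited and the 70 consented as the source of the 56.

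The paragraph in Section 5.1 on the ability to accomplish enrolment and follow-up says that the study rests on approximately 28 evaluable men per arm, "therefore on ≥ 56 evaluable subjects completing the study protocol".

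Flow Chart 3 (Section 4) sets out the same path in stages. At the eye, Holter and laboratory screening it has "n=70; 35 each for the AQ-13 and Coartem groups, expected 5% ineligible". At randomisation it has "n=66; 33 each for the AQ-13 and Coartem groups, expected 20% loss to follow-up". At follow-up it has 28 evaluable per group.

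The statistical section uses another figure. Section 10.2 refers to "approximately 65% of the 26 evaluable subjects in each group". In Table 8 the row for the 15% margin reads 26 per group with no dropout and 33 with 20% dropout.

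**The concern.** Flow Chart 3 attaches the 20% loss to the 33 randomised per arm, and one-fifth off 33 does not leave 28. Section 5.1 hides the step by describing the 70 consenting men as 33 per arm, although two arms of 33 make 66. The men found ineligible between consent and randomisation disappear from the text, and the 20% is in effect taken from the larger number.

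What is at stake is limited but real. The evaluable number is a stated target, and in one place it is given as a lower bound. A trial in which every planning assumption came true would be expected to finish about three men below that bound. A DSMB or ethics committee reading the population section would expect 56 evaluable men, while a reader of the statistical section would expect 52.

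**Working it through.** **Inputs, all from the protocol**
- Consented: 70 (Section 5.1, Flow Chart 3)
- Ineligible after consent: 5% (Flow Chart 3)
- Randomised: 66, that is 33 per arm (Flow Chart 3, Section 10.2)
- Loss: 20%, shown against the 66 randomised (Flow Chart 3) and described in Section 10.2 as attrition after treatment
- Stated yield: 28 per arm, 56 in total (Section 5.1, Flow Chart 3)
- Evaluable number in the statistical section: 26 per group (Section 10.2, Table 8)

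**1. Reproduce the stated figure.** Taking the 20% from the men who consented:

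70 x (1 - 0.20) = 56, and 56 / 2 = 28 per arm.

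This matches exactly, but it skips the 5% ineligibility step.

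**2. Follow the stages as Flow Chart 3 gives them.**

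- After screening: 70 x (1 - 0.05) = 66.5, taken as 66 randomised, 33 per arm.
- After loss: 66 x (1 - 0.20) = 52.8 in total; 33 x 0.80 = 26.4 per arm.

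**3. Size of the gap.**

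- Total: 56 - 52.8 = 3.2 men, which is 5.7% of 56.
- Per arm: 28 - 26.4 = 1.6 men.

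**4. Attrition at which 28 of 33 would be kept.**

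1 - 28/33 = 0.152, that is 15.2%.

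**5. What 28 per arm would need at 20% loss.**

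- Randomised: 28 / 0.80 = 35 per arm, 70 in total.
- Consented: 70 / 0.95 = 73.7, about 74.

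**6. Where the 33 comes from.** Table 8 starts at 26 for the 15% margin: 26 / 0.80 = 32.5, rounded up to 33. The enrolment number was therefore built on 26, not on 28.

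**7. Power, as a caution only.** Take 95% cure in both arms, a 15% margin and the normal approximation, so that power = Φ(0.15 / √(2 x 0.95 x 0.05 / n) - z).

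| Evaluable per arm | One-sided 0.05 | One-sided 0.025 |
|---|---|---|
| 26 | 80% | 70% |
| 28 | 82% | 73% |

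The two-man difference moves power by about 3 percentage points at either level. At the one-sided 0.025 of Section 10.3 neither number reaches 80%; by the same formula 34 evaluable per arm would be needed.

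**The case against.** Several points can be made in the plan's defence.

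- **The 20% is a cautious figure.** Section 10.2 calls it conservative and allows for dropout up to that level. Section 5.1 offers payment and transport to keep men in follow-up. If attrition were about 15% or less, 28 per arm would be reached. This stands. A reader might infer that 56 cannot be met, and the documents do not support that. They support only that it is not the expected result at the 20% planning figure, which Flow Chart 3 labels as expected.
- **The 28 is hedged.** The yield sentence and the enrolment paragraph both say approximately. This stands in part. The target sentence in Section 5.1 and the end box of Flow Chart 3 carry no hedge, and the total is written as at least 56.
- **Nothing in the design depends on 28.** This stands. The 33 per arm comes from 26, the interim look is set at 15 per arm, the final report at 66 enrolled, and the analysis in Section 10.3 does not use 28. A reader might infer that this error leaves the trial short of its planned sample size. It does not: a yield of 26 is what Table 8 asks for.
- **The documents do not say which figure was intended.** Flow Chart 3 shows 35 per arm at screening, which is what 28 would need at 20% loss. But those 35 are counted before the 5% exclusion. Sections 8.6, 10.2 and 14.4 all fix enrolment at 33 per arm, or 66. With enrolment fixed there, the yield that follows is 26.

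**Conclusion.** The point holds as an internal inconsistency in the expected evaluable number. At the protocol's own planning figures the yield is 52.8 men, about 26 per arm, and not the 28 per arm (at least 56 in total) stated in Section 5.1 and Flow Chart 3. The stated number results from applying the 20% to the 70 consented men, and it contradicts Section 10.2 and Table 8. The shortfall is 1.6 men per arm. It alters no enrolment number, test, margin or stopping rule.

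The conclusion assumes that the 5% and 20% are the planning rates and that the 20% acts after randomisation, as Flow Chart 3 and Section 10.2 both indicate.

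A reader might also take a correction to 26 as confirmation that 26 per arm is enough. That does not follow. Whether Table 8 agrees with the one-sided alpha of 0.025 in Section 10.3 is a separate question, and the power figures above suggest that it does not.

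**What to change.** - In Section 5.1 (the target, the yield sentence and the enrolment paragraph) and in Flow Chart 3, restate the expected evaluable number as about 26 per arm, about 52 in total, in agreement with Section 10.2 and Table 8.
- In Section 5.1, separate the 70 men who consent from the 66 randomised (33 per arm) after the 5% found ineligible, and state that the 20% attrition applies to those randomised.
- If the calculation in Section 10.2 is revised to match the one-sided alpha of 0.025 in Section 10.3, rebuild the funnel from the new number instead of from 26.

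The first two changes are wording only. They need no extra patients and leave enrolment as planned; the one cost is a slightly less favourable stated yield.
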